10. DATA MANAGEMENT

Data management will be performed by Duke Clinical Research Institute (DCRI).

The data collected through third party sources will be obtained and reconciled against study data.

The DCRI will be responsible for medical coding. Adverse events will be coded using DCRI's current version of the medical dictionary for regulatory activities (MedDRA) updated semi-annually. Medications will be classified according to the AstraZeneca drug dictionary that AstraZeneca will provide to DCRI.

Data queries will be raised for inconsistent, impossible or missing data. All entries to the study database will be available in an audit trail.

The data will be validated as defined in the Data Management Plan. Quality control procedures will be applied to each stage of data handling to ensure that all data are reliable and have been processed correctly.

When all data have been coded, validated and locked, a clean file will be declared. Any treatment revealing data may thereafter be added and the final database will be locked.

11. EVALUATION AND CALCULATION OF VARIABLES

- **11.1** Calculation or derivation of efficacy variable (not applicable)
- **11.2** Calculation or derivation of safety variable(s)
- **11.2.1** Other significant adverse events (OAE) (not applicable)

11.3 Calculation or derivation of patient reported outcome variables

The EQ-5D data will be used to calculate utility weights based on the UK tariff. The EQ-5D data will be reported in the CSR. To the extent the EQ-5D data is used for health economic modeling this will be reported outside the CSR as part of subsequent health economic analyses. In addition, explorative analyses for differences in health related quality of life between the treatment groups will be performed. These analyses will also be reported separate from the CSR. Descriptive analyses of PAQ data will be reported in the CSR.

- **11.4** Calculation or derivation of pharmacokinetic variables (not applicable)
- 11.5 Calculation or derivation of pharmacodynamic variable(s) (not applicable)
- 11.6 Calculation or derivation of pharmacogenetic variables (not applicable)

11.7 Calculation or derivation of health economic variables

All health care resource utilization data will be carried out as part of the CSR. The health care resource utilization data and the EQ-5D data will be used in combination with cost and life-table data to develop health economic analyses and cost-effectiveness analyses. These analyses will be carried by the HECON Sub-study Team and will be reported independently of the CSR.

12. STATISTICAL METHODS AND SAMPLE SIZE DETERMINATION BY ASTRAZENECA

12.1 Description of analysis sets

12.1.1 Full analysis set (FAS)

All patients who have been randomised to study treatment will be included irrespective of their protocol adherence and continued participation in the study. Patients will be analyzed according to their randomised study medication irrespective of whether the event occurred before or following discontinuation of study medication. Patients who withdraw consent to participate in the study will be included up to the date of their study termination except for vital status known through public records (for use in the analysis of all-cause mortality). All efficacy variables will be analyzed using the FAS.

12.1.2 Safety analysis set

All patients who received at least 1 dose of randomised ticagrelor or clopidogrel, and for whom post-dose data are available will be included in the safety analysis set. Throughout the safety results sections, erroneously treated patients (eg, those randomised to ticagrelor but actually given clopidogrel) will be accounted for in the actual treatment group. If a patient received study drug from the wrong kit for only a part of the treatment duration and then switched to another, the associated actual treatment group for that patient will be the treatment group that patient was randomized to. Patients will be censored at 7 days after their last dose of study medication.

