2.2.1 Other objectives

Other objectives are exploratory with the purpose of comparing other possible long-term treatment effects of ticagrelor vs. clopidogrel in patients with established PAD on:

- Net clinical benefit evaluated by
 - a) The variable is time from randomisation to first occurrence of any event in the following composite of all-cause mortality, MI, ischaemic stroke, ALI or major amputation caused by PAD, and fatal bleeding or intracranial bleeding.
 - b) The variable is time from randomisation to first occurrence of any event in the following composite of all-cause mortality, MI, ischaemic stroke, ALI or major amputation caused by PAD, and TIMI major bleeding.
- the event rate of non-CV death. The efficacy variable is time from randomisation to occurrence of non-CV death.
- the progression of the clinical/symptomatic status of the limb by changes in clinical stage (Rutherford and Fontaine stage).
- The event rate of all amputations. The efficacy variable is time from randomization to occurrence of all amputations caused by PAD
- the event rate of major amputation caused by PAD. The efficacy variable is time from randomisation to occurrence of major amputation caused by PAD.

- the impact on quality of life by collecting health related quality of life data using the Peripheral Artery Questionnaire (PAQ). The PAQ instrument will be administered at all clinics in countries where a validated form is available in local language.
- the primary efficacy and primary safety variable in subgroups of patients with established risk factors for PAD (eg, clinical stage, prior MI, diabetes, hyperlipidemia, tobacco use, etc).
- the event rate of CV-related hospitalisation (including all-cause death, MI, ischaemic stroke, lower extremity revascularisation, major amputation due to PAD, transient ischaemia attack (TIA), coronary revascularisation or unstable angina). The efficacy variable is a) total CV hospital days, and b) time from randomisation to first occurrence of any of these events. Any individual component not already evaluated will also be examined in an analogous manner.

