6.4.3 Recording of adverse events

Time period for collection of adverse events

Only non-serious AEs of interest (ie, bleeding events, dyspnoea, renal impairment/increased creatinine, bradyarrhythmia, increased LFTs, gout/uric acid increases, pneumonia, gynecomastia, abnormal uterine bleeding and all malignancies excluding non-melanoma skin cancers) and DAEs will be collected from time of randomisation throughout the treatment period and including the follow-up period, until the Study Closure Visit.

All SAEs will be recorded from the time of informed consent, with the exception of events defined as disease progression (see Section 6.4.3.1) and those described in Section 6.4.4.1.

SAEs will be recorded at all visits in patients who prematurely discontinue treatment with study medication. Non-serious AEs of interest and DAEs will be recorded until the Study Closure Visit but no less than 30 days after last dose of study medication.

Follow-up of unresolved adverse events

Any non-serious AEs of interest, DAEs and SAEs that are unresolved at the patient's last visit in the study are followed up by the investigator for as long as medically indicated, but without further recording in the eCRF. AstraZeneca retains the right to request additional information for any patient with ongoing AE(s) of interest /SAE(s) at the end of the study, if judged necessary.

Variables

The following variables will be collected and recorded for each **non-serious AE of interest** and **DAE:**

- AE
- the date when the AE started and stopped
- investigator causality rating against the Study Medication (yes or no)
- action taken with regard to study medication
- outcome

In addition, the following variables will be collected and recorded for SAEs:

- SAE (verbatim)
- Date AE met criteria for serious AE
- Date Investigator became aware of serious AE
- AE is serious due to
- Date of hospitalisation
- Date of discharge
- Probable cause of death
- Date of death
- Autopsy performed (if performed)
- Autopsy results
- Causality assessment in relation to Study procedure(s)
- Causality assessment in relation to Other medication
- Description of AE
- Date and time of last dose of study medication before AE

It is important to distinguish between serious and severe AEs. Severity is a measure of intensity whereas seriousness is defined by the criteria in Section 6.4.2. An AE of severe intensity need not necessarily be considered serious. For example, nausea that persists for

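### The only safety analysis set stops at 7 days after last dose, so late non-fatal malignancies and SAEs that the protocol collects fall outside the planned safety analysis

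*Protocol*

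**What the plan says.** Section 12.1 of the protocol defines two analysis sets. The full analysis set (12.1.1) is assigned to the efficacy variables and counts events before or after drug is stopped. The safety analysis set (12.1.2) covers "All patients who received at least 1 dose of randomised ticagrelor or clopidogrel, and for whom post-dose data are available", and its treatment-assignment rule is framed for all safety reporting ("Throughout the safety results sections, erroneously treated patients"). The definition ends: "Patients will be censored at 7 days after their last dose of study medication". Nothing restricts that sentence to bleeding or to any other class of event.

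Section 6.4.3 sets a longer collection window. For malignancies and the other listed events it says "gynecomastia, abnormal uterine bleeding and all malignancies excluding non-melanoma skin cancers) and DAEs will be collected from time of randomisation", and the end of the window is given as "will be recorded until the Study Closure Visit but no less than 30 days after last dose of study medication". After early stopping, "SAEs will be recorded at all visits in patients who prematurely discontinue treatment with study medication". Section 5.8.2 adds that stopping drug does not end follow-up.

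Section 12.2.2 plans Cox models from first dose for the bleeding variables and for discontinuation due to major bleeding, and descriptive summaries for SAEs, DAEs and adverse events of interest. It gives no observation window of its own and no analysis to study closure. The safety objective in section 2.3 concerns long-term therapy.

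**The concern.** A short lag after last dose isolates the effect of a drug whose bleeding risk fades once it is stopped. It does not suit events that develop slowly or are diagnosed late, and the protocol singles out malignancy for collection. If 7 days is the only window, a patient who stops for good in the first months contributes almost nothing to the safety comparison, even though follow-up continues for years.

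The cut is also tied to stopping drug. Where stopping is related to a patient's later risk and differs between arms, such censoring is informative and the comparison of late events may be distorted. Section 12.2.1 plans sensitivity analyses for informative censoring of the primary efficacy endpoint, where patients are followed whatever their drug status. Safety, where the censoring follows drug status directly, has no counterpart. Benefit would then be estimated on an intention-to-treat basis and risk on an on-treatment basis.

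**Working it through.** The plan states no figure on this point, so there is none to reproduce. The check compares the two windows and then sizes the gap.

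**Inputs from the protocol.** Analysis window: 7 days after last dose (12.1.2). Minimum collection window: 30 days after last dose (6.4.3). End-of-treatment visit to Study Closure Visit: 35 ± 5 days (3.1). Expected median duration: 32 months (5.5.2). Patients: about 13,500 (3.1).

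**Assumed input.** Premature permanent discontinuation by 32 months: 10% to 40%. The protocol gives no rate.

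**Window after last dose.**
- Minimum window: (30 − 7)/30 = 23/30 = 77% collected but outside the analysis.
- Patients on drug to the end, taking last dose as the end-of-treatment visit: (35 − 7)/35 = 28/35 = 80%.

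**One patient who stops for good at month s.** With T = 32 months and w = 7/30.44 = 0.23 months, the excluded share is (T − s − w)/T.
- s = 3: (32 − 3 − 0.23)/32 = 90%.
- s = 12: (32 − 12 − 0.23)/32 = 62%.

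**All patients.** With discontinuation at a constant hazard, λ = −ln(1 − d)/T, where d is the proportion stopped by T. Mean excluded time per patient is the integral of λe^(−λt)(A − t) from 0 to A = T − w, which equals A − (1 − e^(−λA))/λ. For d = 0.20: λ = 0.2231/32 = 0.00697 and A = 31.77, giving 3.27 months, and 3.27/32 = 10.2%. Total follow-up is 13,500 × 32/12 = 36,000 patient-years.

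| Assumed d | Months excluded per patient | Share of follow-up | Patient-years (× 13,500/12) |
|---|---|---|---|
| 10% | 1.61 | 5.0% | about 1,800 |
| 20% | 3.27 | 10.2% | about 3,700 |
| 30% | 5.02 | 15.7% | about 5,600 |
| 40% | 6.85 | 21.4% | about 7,700 |

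Earlier stopping raises the share: if the same 20% all stopped at month 3, it would be 0.20 × 90% = 18%. Withdrawal of consent lowers what can be recovered, because only vital status is then sought (5.8.3.3, 5.9). The table is therefore follow-up outside the analysis, not a count of fully collected time.

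**What is still counted elsewhere.** Late deaths up to the primary analysis censoring date enter all-cause mortality (12.2.1) and non-CV death (2.2.1). Late TIMI major, fatal or intracranial bleeds enter the exploratory net-benefit composites, for which section 2.2.1 says "The variable is time from randomisation to first occurrence of any event in the following composite of all-cause mortality". A late haemorrhagic stroke also counts in the fifth secondary endpoint. Late non-fatal malignancies and other late non-fatal SAEs that are not efficacy endpoints have no planned analysis.

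**The case against.** Collecting more than one analysis uses is not a contradiction. The longer window also serves expedited SAE reporting and DMC review, so a reader who infers that the data are thrown away goes too far: they are recorded and available.

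Censoring is a time-to-event term, and section 12.2.2 reserves time-to-event methods for bleeding and for discontinuation due to bleeding. Applying the cut to descriptive adverse event tables is a reading of the set definition, and windows for such tables are often left to a statistical analysis plan. This has force. But the sentence sits unqualified in the definition of the only safety set, and no other window is offered, so at the least its scope needs stating.

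An on-treatment window is also a defensible choice. Patients who stop for good move to conventional therapy, so later time mixes exposures. That stands for bleeding, and the proposal leaves the bleeding analysis as it is. Stopping for a bleed need not be final either: section 5.8.1 lists major bleeding under temporary discontinuation and section 6.4.5.2 allows drug to be resumed. The gap concerns permanent discontinuation.

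A reader might further infer that the rule will hide an excess of harm on ticagrelor. The protocol does not establish that. Section 1.4 cites an earlier acute coronary syndrome trial with more non-procedural major bleeding on ticagrelor (3.1% vs 2.3%, HR 1.31), no difference in total major bleeding, and dyspnoea as an observed event. These make unequal stopping plausible, but none is a discontinuation rate. Nor can a number of missed malignancies be derived: no malignancy rate is given, and a count pooled over both arms would say nothing about bias between them.

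**Conclusion.** The point holds as a weakness in how the safety window is fixed. As written, one on-treatment window of 7 days governs a long-term safety assessment, and non-fatal malignancies and other late non-fatal SAEs after permanent discontinuation lie outside it although sites are asked to record them. The size depends on a rate the protocol does not give: about 5% to 21% of follow-up for 10% to 40% discontinuation, assuming a constant hazard and 32 months for every patient. Informative censoring is a conditional risk that arises if stopping differs by arm; it is not a demonstrated bias. The primary bleeding analysis and the mortality endpoints are not called into question. The change is worth making because it is cheap and uses data already planned.

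**What to change.** Keep the 7-day on-treatment analysis as primary for bleeding. In 12.1.2, state which analyses the 7-day rule governs, including whether it applies to the descriptive adverse event tables. In 12.1.2 and 12.2.2, add that treated patients are also analysed by randomised arm, from first dose to the Study Closure Visit, regardless of study drug status. Apply this to SAEs and malignancies and, as a sensitivity analysis, to TIMI major bleeding. Make the to-closure analysis the main one for malignancy.

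The cost is a wording change and a second set of tables, with no new visits, data or patients. The drawback is that off-drug time dilutes acute effects, which is why the on-treatment analysis stays primary for bleeding.

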12.2 Methods of statistical analyses

12.2.1 Efficacy analysis

All efficacy analyses will be based on the intent-to-treat principle using the FAS, including only events adjudicated by the CEC. Investigators are instructed to report all suspected endpoints in the eCRF, even those that may not meet strict endpoint definitions, to ensure all potential events are reviewed and adjudicated by the CEC. The time from randomisation to the first occurrence of any event in the given endpoint will be compared using the Cox proportional hazards model with a factor for treatment group. The p-value, HR, and 95% confidence interval will be reported. No multiplicity adjustment will be made to the confidence intervals, as they will be interpreted descriptively and used as measures of precision. Kaplan-Meier estimates of the cumulative risk of each composite endpoint and its individual components will be calculated and plotted.

Primary efficacy variable:

The primary analysis will compare the time from randomisation to the first occurrence of any event in the composite endpoint CV death, MI and ischaemic stroke. Refer to Appendix E for definitions of CV death, MI and ischaemic stroke.

The null hypothesis will be that the risk/hazard of an event on ticagrelor is equal to the corresponding risk/hazard on clopidogrel:

 H_0 : HR (ticagrelor divided by clopidogrel) = 1

The alternative hypothesis will be that the HR is greater, or less than 1:

H₁: HR \neq 1

The hypothesis will be tested at 4.94% two-sided significance level to account for the single planned interim analysis with the overall type I error preserved at 5%. If the DMC conducts additional interim analyses of the primary outcome, these levels will be adjusted accordingly using the alpha spending function. For definition of the significance level of the final analysis, see Section 12.2.3.

The HR and 95% confidence interval will be reported. Kaplan Meier estimates of the cumulative incidence to the first occurrence of any event in the composite endpoint will be calculated and plotted, as will the cumulative risk to the first occurrence of each component separately. The contribution of each component of the primary composite efficacy endpoint to the overall treatment effect will be examined.

The assumption of proportional hazards for the factor for treatment group will be assessed visually using log-cumulative hazard plots. The effect of any departures from proportional hazards will be discussed as part of the presentation of results of the analyses. An additional explorative analysis of the primary endpoint with cardiovascular death replaced by all-cause mortality will be performed.

To assess possible effects of informative censoring, sensitivity analyses will be done as follows. Based on the missing follow-up time in drop-outs, ie, the time from censoring to primary analysis censoring date, the expected number of events that might have been observed if all patients would have completed the study can be calculated using an event rate similar to that observed in the study. The comparison of ticagrelor and clopidogrel will be recalculated with these residual events allocated in different proportions to the treatment groups to assess the robustness of the results with regard to patients who are censored prior to the primary analysis censoring date.

Subgroup analysis will be performed to evaluate variation of treatment effect, as well as a test of interaction with treatment for each subgroup variable. The p-values of the subgroup analyses and interaction tests will not be adjusted for multiple comparisons as the tests are exploratory and will be interpreted descriptively. Hazard ratios and 95% confidence intervals will be reported for each subgroup. Subgroup analyses will be performed on the primary efficacy and safety variables.

Subgroup analysis will be performed based on whether a patient had a prior MI (as defined in Section 4 and the eCRF) at baseline. In addition, the subgroup analysis will be performed based on a patient's Fontaine scale at baseline. Patients with Fontaine scale II will define one subgroup while patients with Fontaine scale III and IV will form the other. For the subgroup analysis of geographic regions, the four geographical regions will be:

Clinical Study Protocol Drug Substance Ticagrelor Study Code D5135C00001 Edition Number 2 Date 3 Mar 2015

- Europe/Africa
- Asia/Oceania
- North America
- Central/South America

Additional subgroup analyses will include age, sex, race, weight/BMI, prior antiplatelet therapy, medical history characteristics (eg, risk factors for developing atherothrombosis and risk factors for bleeding), revascularization history and history of coronary stent implantation.

Secondary efficacy variables

The analysis of the primary composite variable will be repeated for the secondary efficacy variables, which are in order

- 1. time from randomisation to first occurrence of any event in the composite of CV death, MI, ischemic stroke and ALI
- 2. time from randomisation to occurrence of CV death
- 3. time from randomisation to occurrence of MI
- 4. time from randomisation to occurrence of all-cause mortality
- 5. time from randomisation to occurrence of composite of CV death, MI, and all-cause Stroke (ischaemic or haemorrhagic)
- 6. time from randomisation to occurrence of ALI
- 7. time from randomisation to occurrence of lower extremity revascularization
- 8. time from randomisation to occurrence of any revascularisation (coronary, peripheral [limb, mesenteric, renal, carotid and other])

The analysis of the primary and the eight secondary efficacy variables will comprise the confirmatory analysis. In order to address the issue of multiple testing a hierarchical test sequence will be used.

Only if the treatment effect on the primary efficacy variable is significant at the 4.94% level, will the secondary efficacy variables be tested in a confirmatory sense in the order given above. The hypothesis testing will continue at the 4.94% significance level until the first statistically non-significant treatment difference ($p \ge 0.0494$) is observed. Secondary efficacy variables following in the sequence after the first non-significant test will be tested in an

exploratory manner. The results for objectives in Section 2.2 that are not part of the confirmatory analysis will be presented descriptively. Appropriate methods for time-to-event, continuous and categorical data will be used, with further details provided in the Statistical Analysis Plan. For objectives related to PROs further information is provided in Section 6.5, while for objectives related to Health Economics, further information can be found in Sections 6.9 and 11.3.

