12.2.2 Safety variables

Analysis of time from first dose of study medication to each of the following endpoints will be performed

- the first TIMI major bleeding event (primary safety variable)
- the first TIMI major or minor bleeding event
- the first PLATO major bleeding event
- discontinuation of study medication due to any major bleeding event

The assessment of time to bleeding will focus on the items above but will also include analysis of time to first event for additional categories of bleeding according to the TIMI, PLATO, BARC and ISTH definitions. Treatment groups will be compared using the Cox proportional hazards model with a factor for treatment group. Kaplan-Meier estimates of the cumulative incidence of each event will be calculated and plotted and 95% confidence intervals for the hazard ratios presented. The safety assessment will also include analysis of total major bleeding events, fatal bleeding events, fatal or life threatening bleeding events, combined major and minor bleeding events separately. Exploration of potential risk factors for bleeding events, including subgroups and use of concomitant antithrombotic therapy, will be performed.

Bleeding events will be analyzed according to TIMI and PLATO bleeding definitions adjudicated by the CEC (see the CEC charter). BARC and ISTH bleeding profiles will be captured for each patient where appropriate but will not be formally adjudicated (Mehran 2011, Schulman 2005).

Non-serious AEs of interest, DAEs as well as SAEs will also be evaluated. MedDRA will be used for the coding and classification of AEs and SAEs in the database. AEs will be summarised by system organ class and preferred term using MedDRA. Summaries will be presented by treatment group using descriptive statistics. All AEs relating to bleeding will be summarised separately and the total number of bleeding events will be assessed. Exploration of potential risk factors for AEs that are increased with ticagrelor dosing may be done.

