12.2.4 Censoring

The Executive Committee will monitor the accrual of the number of primary events and when appropriate predict and define a primary analysis censoring date at which time the pre-defined target number of events for the primary composite endpoint are expected to have occurred.

The primary analysis censoring date will be the common date at which all patients who are event free for the given endpoint and have not withdrawn consent for participating in the study will be censored in efficacy time-to-event analyses. Events that occur after the primary analysis censoring date but before the ESTV will also be collected and adjudicated. These events may be included in sensitivity analyses but not in the primary analysis.

Patients who have not had the event(s) in question will be censored at the earlier of (1) the primary analysis censoring date and (2) the last study contact when all components of the endpoint in question were assessed. In the analysis of CV death and composites including CV death censoring will occur at the earliest of (1), (2) and the date of death from non-cardiovascular causes. For endpoints not including death, all deaths are censoring events.

Complete endpoint information will be pursued with every effort for all patients regardless of their study medication status, unless they exercise their right to withdraw consent. Patients who have a non-fatal event will continue study follow-up. For patients who withdraw consent and for whom only vital status (known to be alive at study closure, or date of death) may be obtained from public records, the occurrence of all components of the primary endpoint cannot be assessed. Thus the primary endpoint and its components ischaemic stroke, MI, and CV death will be censored at the time of consent withdrawal for those patients who withdraw consent and for whom only vital status is known from public records. However, the determination of all-cause mortality as a sole outcome event will utilise all publicly known mortality data, even that extending beyond date of consent withdrawal. The vital status information will be included in the analysis of all-cause mortality as a single secondary endpoint, in sensitivity analyses and tabulations.

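### Kaplan-Meier curves that censor competing deaths are called cumulative incidence, so the reported absolute risks are biased upward in each arm; the Cox hazard ratios and tests are not affected

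*Protocol*

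**What the plan says.** Three parts of the protocol together settle estimator, label and censoring.

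- **Estimator and label, efficacy (Section 12.2.1).** For endpoints generally: "Kaplan-Meier estimates of the cumulative risk of each composite endpoint and its individual components will be calculated and plotted". For the primary composite: "Kaplan Meier estimates of the cumulative incidence to the first occurrence of any event in the composite endpoint will be calculated and plotted". For the eight secondary endpoints: "The analysis of the primary composite variable will be repeated for the secondary efficacy variables". That list includes MI, ALI, lower extremity revascularisation and any revascularisation.
- **Censoring, efficacy (Section 12.2.4).** For CV death and composites that include it, "censoring will occur at the earliest of (1), (2) and the date of death from non-cardiovascular causes", where (1) is the primary analysis censoring date and (2) is the last contact at which all components were assessed. For the rest: "For endpoints not including death, all deaths are censoring events".
- **Bleeding (Sections 12.2.2 and 12.1.2).** "Kaplan-Meier estimates of the cumulative incidence of each event will be calculated and plotted". The safety analysis set carries its own rule: "Patients will be censored at 7 days after their last dose of study medication". No separate rule for death is given there.

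The protocol names no competing-risk estimator. Section 12.2.1 does plan an exploratory analysis of the primary composite with all-cause mortality in place of CV death.

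**The concern.** A patient who has died of cancer cannot later have an MI or a limb revascularisation. Censoring that patient makes Kaplan-Meier treat them as if they remained at the same risk as those still alive. One minus Kaplan-Meier then describes a hypothetical population in which the competing death does not happen. The cumulative incidence, meaning the proportion of randomised patients who actually have the event by a given time, is lower. The label and the quantity therefore do not match.

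What is at stake is the set of absolute risks read from the curves, in both arms. The confirmatory comparison is not at stake: censoring a competing death is the correct handling for a cause-specific Cox hazard ratio.

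**Working it through.** **1. Figures the plan states.** The protocol gives no cumulative incidence to reproduce. Its event targets do reproduce. With HR 0.85 and two-sided alpha 0.0494 (Section 12.2.1: "The hypothesis will be tested at 4.94% two-sided significance level to account for the single planned interim analysis"), 1:1 allocation and events = 4(z₁₋α/₂ + z_power)² / (ln HR)²:

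- 90% power: 4(1.9651 + 1.2816)² / (ln 0.85)² = 1596.4 (plan: 1596)
- 85% power: 4(1.9651 + 1.0364)² / (ln 0.85)² = 1364.4 (plan: 1364)

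Sample size and power are therefore not in question.

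**2. Inputs.** From the protocol: pooled primary event rate about 4.1% (Section 12.3, read here as per year); expected median duration 32 months and follow-up to about 40 months (Section 5.5.2). Assumed, because the protocol gives none: non-CV death 0.5% to 3% per year; all-cause death 2% to 5% per year; rates of 0.5% to 4% per year for endpoints without death.

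**3. Formulas.** Constant hazards, l for the event and m for competing death, t in years:

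- One minus Kaplan-Meier with deaths censored: 1 − exp(−l·t)
- Cumulative incidence, the quantity Aalen-Johansen estimates: l/(l+m) × [1 − exp(−(l+m)·t)]

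With m > 0 the second is always the smaller. Example for the primary endpoint, l = 0.041, m = 0.03, t = 32/12: Kaplan-Meier 1 − exp(−0.1093) = 10.36%; cumulative incidence 0.041/0.071 × [1 − exp(−0.1893)] = 9.96%.

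**4. Primary composite, l = 0.041.**

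| Time | Non-CV death per year | 1 − KM | Cumulative incidence | Excess, points | Excess, relative |
|---|---|---|---|---|---|
| 32 months | 0.5% | 10.36% | 10.29% | 0.07 | 0.7% |
| 32 months | 3% | 10.36% | 9.96% | 0.40 | 4.0% |
| 40 months | 0.5% | 12.77% | 12.67% | 0.10 | 0.8% |
| 40 months | 3% | 12.77% | 12.17% | 0.60 | 5.0% |

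**5. Endpoints without death.** Over event rates of 0.5% to 4% and all-cause death of 2% to 5% per year, the excess is 2.6% to 6.8% relative at 32 months (0.03 to 0.63 points) and 3.3% to 8.5% at 40 months (0.05 to 0.96 points). The relative excess depends mainly on the death rate and hardly on the event rate.

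**6. Between-arm contrast, equal competing mortality.** HR 0.85 and a pooled 4.1% give hazards of 0.041 × 2/1.85 = 0.0443 and 0.85 × 0.0443 = 0.0377. At 32 months the risk difference is 1.59 points by Kaplan-Meier against 1.57 to 1.53 by cumulative incidence (non-CV death 1% to 3% per year). The risk ratio is about 0.857 by either.

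**7. Between-arm contrast, unequal competing mortality (illustration).** Take a non-fatal endpoint with control hazard 0.05 per year, control mortality 0.03 to 0.05 per year, and a mortality HR of 0.78. The last matches the numerical 22% all-cause mortality reduction that Section 1.3 cites from the earlier acute coronary syndrome trial. At 32 months:

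- Event HR 0.85: difference 1.77 points by Kaplan-Meier, 1.61 to 1.52 by cumulative incidence; 1.77/1.61 = 1.10 and 1.77/1.52 = 1.16.
- Event HR 1.0: difference zero by Kaplan-Meier; cumulative incidence is 0.10 to 0.17 points higher on ticagrelor, because more patients survive to have the event.

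**The case against.** The strongest reply is that nothing decisive uses these curves. The confirmatory analysis rests on the Cox hazard ratio and p-value, and no stopping rule, success criterion or event target depends on a Kaplan-Meier estimate. That stands. It limits the importance of the point but does not make the label correct.

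The reply can also say that the size rests on assumed death rates, that the primary-endpoint bias is tenths of a point, and that contrasts barely move when competing mortality is equal. All of this stands. Equal mortality is not guaranteed, however: CV death and all-cause mortality are themselves endpoints on which the trial looks for a difference.

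The analysis with all-cause mortality in place of CV death removes the competing risk for that one composite. It does nothing for MI, ALI or revascularisation. The informative-censoring sensitivity analysis in Section 12.2.1 concerns drop-outs, not competing deaths. The statistical analysis plan, which is not at hand, may add a cumulative incidence function, but the estimator, the label and the censoring rule are already fixed in the protocol.

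Three stronger readings are tempting and not supported:

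- **Cost-effectiveness results will be inflated.** Sections 6.9 and 11.7 describe resource-use and EQ-5D data combined with external cost and life-table data. Nothing says that Kaplan-Meier risks enter that work.
- **Net clinical benefit is biased.** Both composites defined in Section 2.2.1 contain all-cause mortality, so no death competes and Kaplan-Meier is valid for them.
- **Bleeding incidence is wrong in the same way.** The rules in Section 12.2.4 are for efficacy analyses. The bleeding curve is cut off 7 days after the last dose and so describes on-treatment risk; fatal bleeds count as events. Censoring of other deaths follows from the method, not from a stated rule, and a competing-risk estimator alone would not turn the curve into bleeding incidence over full follow-up.

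**Conclusion.** The point holds as a mismatch between estimator and label that biases the reported absolute efficacy risks upward in each arm. The direction is certain whenever competing deaths occur. The size depends on assumed constant death rates: about 0.07 to 0.6 percentage points for the primary composite over 32 to 40 months, and about 3% to 9% relative for MI, ALI and revascularisation.

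A reader might infer that the primary result or the planned risk differences are compromised. They are not: Cox hazard ratios, p-values, alpha, the hierarchy and the event target are untouched, and Section 12 plans no risk-difference estimate. Differences that readers take from the curves change little if competing mortality is equal across arms and can shift if it is not. The point is worth correcting because the curves are how absolute risk will be read, but it is a reporting correction and not a threat to the confirmatory conclusion.

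**What to change.** - **Section 12.2.1.** Report and plot the Aalen-Johansen cumulative incidence, with any death not in the endpoint as a competing event, for every efficacy endpoint that does not contain all-cause death. Non-CV death competes for CV death and its composites; all deaths compete for MI, ALI and revascularisation.
- **Keep** the cause-specific Cox model for hazard ratios and p-values, and the Section 12.2.4 censoring that serves it.
- **Keep** Kaplan-Meier for all-cause mortality and for composites that contain it: the net clinical benefit composites, the CV-related hospitalisation composite and the exploratory primary composite with all-cause death.
- **Section 12.2.2.** For bleeding, either treat non-bleeding death as a competing event or label the curve as an on-treatment Kaplan-Meier estimate. In either case note the censoring at 7 days after the last dose.

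The cost is a few lines of text, a standard procedure call and slightly lower reported risks. Section 6.3.1 already has all post-randomisation deaths recorded and adjudicated, so no further data are needed.
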